## Study Synopsis

OBJECTIVE	The objective of the study is to actively gather additional information on the use of CorMatrix ECM for pericardial reconstruction.
STUDY POPULATION	Up to 100 clinical sites will enroll subjects who have received CorMatrix ECM for pericardial reconstruction.
INDICATIONS FOR USE	The CorMatrix ECM for Pericardial Closure is intended for the reconstruction and repair of the pericardium.
ENDPOINTS	The endpoint is defined as the proportion of subjects with device related adverse events.
EXAMINATION SCHEDULE	One single post-operative visit following pericardial reconstruction with the CorMatrix ECM.
CLINICAL PARAMETERS	
The following clinical data will be collected at a single post-operative visit:
 

• Demographic information

• Pre-operative risk factors

• Surgical procedure

• Blood transfusion information, if applicable

• Chest tube placement information

• Surgical complications

• Use of anticoagulation medication

• Cardiac related procedures since surgical procedure

• Device related adverse events

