#### ***4.2 Post-market Clinical Evaluation of the ECM for Carotid Repair***

CorMatrix is currently conducting a post-market registry study for the CorMatrix ECM for Carotid Repair (Protocol No. 11-PR-1021). The objective of this registry is to capture and assess device performance data from subjects undergoing patch angioplasty of the carotid artery following carotid endarterectomy using the CorMatrix ECM for Carotid Repair per its commercial Indications for Use. This registry provides an ongoing post-market surveillance mechanism to document clinical outcomes on the use of the CorMatrix ECM for Carotid Repair. This is a multi-center, prospective, single-arm, post-market, observational registry of subjects receiving the CorMatrix ECM for Carotid Repair for patch angioplasty following carotid endarterectomy procedures. This post-market registry may involve up to ten U.S. clinical sites and up to 230 subjects. Data will be collected through the 24-month follow-up.

One-hundred and eighty six patients are enrolled in the study and included in the interim analysis of the CorMatrix ECM for Carotid Repair registry. The data demonstrated that the rate of device related adverse events were consistent with the rates found in the review of the contemporary literature for patch angioplasty. Specifically, no unanticipated events were found and the rate of the events was as anticipated in the risk management plan. Of specific interest in the analysis was the rate of pseudoaneurysm, which was present in 2 (1.08%) of the 186 patients and compared favorably to the rates found in the literature (1.4% to 5%).

The mean carotid stenosis (maximum) at pre-operative was 84.8%. Mean change from baseline values were -56.8%, -57.9%, and -59.6% at the 1 to 3-month, 6-month, and 12-month follow-up evaluations. The mean carotid stenosis (minimum) at pre-operative was 71.7%. Mean change from baseline values were -63.9%, -61.2%, and -63.4% at the 1 to

3-month, 6-month, and 12-month follow-up evaluations. No data are yet available for the 24-month follow-up evaluation, as the first enrollment was on May 24, 2012.

As a result of this analysis and the directed and ongoing risk management activities, the overall residual risk of the CorMatrix ECM for Carotid Repair is determined to be acceptable.

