## **6. Study Design**

This is a multi-center post-market observational study. It is anticipated that 100 or more eligible centers will participate. There is no upper limit for the number of enrolled subjects. Eligible candidates will be approached to ascertain interest in study participation at their initial follow up visit. If a subject has had CorMatrix ECM used in their surgery they will be asked to allow their physician to use their medical information from the surgical procedure and the current visit. All elements of the approved informed consent will be provided verbally and the process will be documented in the subject study binder by the research staff. A copy of the consent will be provided to the participant. This study includes a one-time visit at the initial post-operative visit.

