## ***10.2 Assessing and Recording Adverse Events***

Each AE recorded must be documented on the Case Report Form. All serious and device related events must be reported immediately to CorMatrix via telephone or email within 24 hours of the Investigator becoming aware of the event. The case report form will be submitted to CorMatrix. The site will be contacted by CorMatrix for additional information including, but not limited to:

- Description of the event and underlying cause (diagnosis), coexisting disease, or other.
- Date of onset and date of resolution. If the event is present at the single post-operative visit it will be marked as unresolved.
- Intensity of the event: mild, moderate, or severe.
- Frequency of the event: single episode, intermittent, or continuous.
- Action taken: none, medication, procedure, medication and procedure, or other.
- Relationship to the procedure/surgery: not-related, possibly-related, or probably-related.

The Investigator must ensure that the details of the event are documented in the medical notes including full details of the outcome, in addition to recording the event on the appropriate case report form.

Serious adverse events and/or device related events contact information at CorMatrix:

[name]  
Quality Systems Manager, CorMatrix  
[contact]  
[[contact]](mailto:[contact])

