## **11. Data Analysis**

Since this is a post-market study, analyses will consist of tabulated data and descriptive statistics. Subject data listings and tabular and graphical presentations of the summary and statistical results will be provided. Additional quantitative and qualitative comparisons will be made to contemporary literature and similar studies

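### Do the conflicting site numbers and the unstated data cut call for a change to the plan?

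*Protocol*

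**What the plan says.** **Number of sites.** The Study Synopsis, under study population, states: "Up to 100 clinical sites will enroll subjects who have received CorMatrix ECM for pericardial reconstruction". Section 6 (Study Design) states: "It is anticipated that 100 or more eligible centers will participate".

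**Number of subjects.** Section 6 continues: "There is no upper limit for the number of enrolled subjects". The Protocol gives no target, minimum, enrolment closing date or data cut.

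**Endpoint and analysis.** Section 5 has a single endpoint, the proportion of subjects with device related adverse events. Section 11 limits the analysis to tabulations and descriptive statistics, and adds: "Additional quantitative and qualitative comparisons will be made to contemporary literature and similar studies". There is no hypothesis, significance level, margin or performance goal. Section 1 says the data will support neither a marketing claim nor a labeling change.

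**What the sponsor sees during the study.** Section 10.2 requires: "All serious and device related events must be reported immediately to CorMatrix via telephone or email within 24 hours". The clock starts when the investigator becomes aware of the event. Case report forms go to the sponsor by email or mail (Section 9).

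**A related precedent.** Section 4.2 describes the sponsor's carotid registry: "This post-market registry may involve up to ten U.S. clinical sites and up to 230 subjects". It was reported before reaching that number: "One-hundred and eighty six patients are enrolled in the study and included in the interim analysis". Its event rates were set against published ones.

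**The concern.** There are two separate worries.

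1. The Synopsis reads as a cap on sites and Section 6 as an expectation of reaching or passing that same number. A review board or a prospective 101st site could not tell from the text whether that site is allowed.

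2. Enrolment is open-ended, the sponsor sees events as they accrue, and the results are to be compared with literature. If the time of reporting were chosen after looking at the running proportion, the reported figure would be too low on average. The carotid registry shows that the sponsor has compared accruing data with literature before. At stake would be a misleadingly favourable device related event rate in a report or publication.

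**Working it through.** **Site numbers.** Let S be the number of participating sites. The Synopsis gives S ≤ 100; Section 6 anticipates S ≥ 100. Both hold only at S = 100, so the wording does conflict. The next question is what depends on S. The endpoint is a proportion over subjects, Section 11 has no site-level analysis, and there is no sample size calculation. No result changes with S.

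**Data cut: the plan's own figure.** There is none to reproduce. The Protocol states no expected rate, sample size, precision or threshold.

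**Data cut: how large the effect could be.** An exact binomial calculation gives a sense of scale. All inputs are assumptions:
- true rate p, and a threshold t below it;
- looks at cumulative sample sizes n₁ < n₂ < … up to 1,000;
- stopping and reporting at the first look where X/n ≤ t, and otherwise reporting at n = 1,000.

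The 3.9% used for p is the composite safety rate in the ECM group of the earlier randomized trial (Section 4.1). It is not a device related event rate. The other values of p are illustrative.

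The count of events is carried forward from look to look by adding a binomial (nₖ − nₖ₋₁, p) increment. Paths that meet the threshold are removed at each look. The mean reported rate is the sum of X/n over all end points, weighted by their probabilities.

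| True rate / threshold | Every 50 from 100 | Every 50 from 186 | Every 100 from 300 | Every 100 from 500 |
|---|---|---|---|---|
| 3.9% / 3.0% | 3.10% | 3.42% | 3.61% | 3.77% |
| 2.0% / 1.5% | 1.41% | 1.63% | 1.77% | 1.89% |
| 5.0% / 4.0% | 4.09% | 4.46% | 4.67% | 4.86% |

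The relative understatement is (p − mean)/p:
- largest: (2.0 − 1.41)/2.0 = 0.295, about 30%;
- smallest: (5.0 − 4.86)/5.0 = 0.028, about 3%.

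In the 3.9% row the chance of meeting the threshold is 59.8%, 44.7%, 36.2% and 24.2% across the four schedules. The first look alone supplies 45.0, 26.4, 26.5 and 17.9 percentage points of these. Most of the effect is therefore small-sample variation at whatever first look is assumed.

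**The carotid figure.** Section 4.2 reports pseudoaneurysm in 2 of 186 patients: 2/186 = 1.08%, with an exact (Clopper-Pearson) 95% interval of 0.13% to 3.83%. At a true rate of 1.4%, the low end of the quoted literature range, P(X ≤ 2 | n = 186) = 0.516. This shows how imprecise one early result is. It does not show that the time of analysis was chosen because of the rate.

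**Does the Protocol describe the assumed behaviour?** Section 6 leaves enrolment open, Section 10.2 sets prompt safety reporting and Section 11 plans description. None of them sets a threshold, a schedule of looks or a rule that stops or reports on the observed proportion.

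**The case for a change.** The best case for a change is that when enrolment ends is a matter of design, not only of analysis, and the Protocol answers it by leaving enrolment open. The sponsor receives both the event reports and the case report forms, so it can follow numerator and denominator. Section 1 says the study will evaluate safety and effectiveness, and Section 12.3 foresees publication, so a favourably timed figure could mislead readers even with no test and no labeling use. The remedy would be cheap: one site figure in both places, and one sentence fixing the cut independently of the observed rate.

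Part of this stands. The site wording is inconsistent and no statistical analysis plan would cure it. The arithmetic is also sound: selecting on the running rate biases the estimate downward.

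The rest does not establish a fault in the Protocol:
- A data cut commonly belongs in the statistical analysis plan. That document is not shown, so silence here does not mean that no cut is fixed.
- The 24-hour rule is ordinary safety reporting. In an unblinded single-arm observational study the sponsor will see accumulating data anyway, and the rule delivers event reports, not a rate. The denominator arrives on forms for which no deadline is stated.
- Section 11 does not name the event proportion as the quantity to be compared, although it is the only endpoint.
- The carotid registry concerns another product, and its 2/186 is one event type. Section 4.2 does not say why it was analysed at 186.

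**Conclusion.** No change to the plan follows.

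The site numbers are a clerical inconsistency with no numerical effect. They can be aligned whenever the text is next edited. Section 6 is worded as a forecast, not a requirement, and no analysis depends on either figure.

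The data cut is a detail that analysts ordinarily fix before reporting. Leaving subject numbers open is a deliberate and reasonable choice for a descriptive post-market study. Following the Protocol as written gives no wrong result, because nothing in it makes the reporting time depend on the observed rate.

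The 3% to 30% understatement is a conditional illustration. It requires stopping at the first favourable look, and its size is driven mainly by the assumed look schedule. It is not an estimate of bias in this study.

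This conclusion rests on two conditions: that the analysis remains descriptive, as Section 11 says, and that no document at hand links closure or reporting to the running rate. A statistical analysis plan that made such a link would reopen the question.

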## **1. Introduction and Rationale**

Open heart surgery requires opening the pericardium to gain access to the heart structures. Once divided, the pericardium retracts significantly and an inflammatory response starts in the body signaling a change has occurred. Following surgery, the pericardium is difficult to re-approximate and is typically left open to avoid causing undue pressure on underlying grafts and structures. However, the absence of the pericardial barrier often leads to scarring and the formation of adhesions between the heart and the sternum. Moreover, the normal function of the pericardium is compromised. Available synthetic materials have largely been abandoned for pericardial closure because they have been shown to cause more adhesions, calcifications and infections.

The CorMatrix ECM for Pericardial Closure acts as an acellular natural scaffold for repairing the pericardium following cardiac surgery. The acellular ECM scaffold allows the patient's own cells to migrate and attach within the ECM to naturally repair the pericardium.

CorMatrix Cardiovascular, Inc. received FDA 510(k) premarket clearance for the CorMatrix ECM for Pericardial Closure (K051405) on August 31, 2005. This post market observational study will evaluate the safety and effectiveness of CorMatrix ECM for pericardial reconstruction by collecting specific data at the first post-operative visit. Data collected from this study will not be used to support a marketing claim or change in labeling. This study is being performed to gather post-market data only and is not being performed under the direction of the FDA. This study is of minimal risk and involves no procedures for which written consent is usually required.

## **2. Indication for Use**

The CorMatrix ECM for Pericardial Closure is intended for the reconstruction and repair of the pericardium. The entire Instructions for Use (IFU) can be found in Appendix B.

## **3. Description**

The CorMatrix ECM for Pericardial Closure is an extracellular matrix (ECM) scaffold derived from porcine small intestinal submucosa (SIS). CorMatrix has licensed the technology to implement SIS material for use in cardiac surgery. SIS is a natural collagen construct derived from a select layer of tissue that is recovered from porcine small intestine. During processing, the inner and outer muscle layers of the intestine are removed, leaving an intact, acellular, submucosa with a portion of the tunica propria layer attached to the inner surface. The current CorMatrix ECM application for circumferential pericardial reconstruction and repair has demonstrated the same remodeling characteristics in the pericardium as other tissues in various animal models. After several months, cells infiltrate into the matrix with a lack of inflammation, lay down a neo-mesothelial lining and reconstitute a barrier between the heart and surrounding structures. The SIS slowly remodels and is replaced over time by host tissue. Based on the properties of the SIS material, SIS is

well suited to replace the area left open in the pericardium following open heart surgery. The CorMatrix ECM for Pericardial Closure is supplied in a lyophilized, sterile state and is for single use only. The CorMatrix ECM can be cut to the appropriate size, using aseptic technique, in order to adequately cover the pericardial defect.

## 4. Prior Clinical Evaluations

CorMatrix ECM has been studied in previous prospective clinical evaluation, and a post-market clinical study is ongoing. The ECM for Pericardial closure has been studied in a randomized, prospective study to evaluate its ability to reduce the incidence of new onset atrial fibrillation; the ECM for Carotid Repair is under evaluation in a post-market study to capture and assess device performance data from subjects undergoing patch angioplasty of the carotid artery following carotid endarterectomy using the product per its FDA-cleared Indications for Use.

### *4.1. Clinical Evaluation of the ECM Pericardial Closure Device*

The CorMatrix ECM Pericardial Closure device was evaluated in a multicenter, prospective, randomized, controlled clinical study, to demonstrate the safety and effectiveness of the device to reduce the incidence of new onset postoperative atrial fibrillation by circumferentially reconstructing the normal pericardial anatomy following isolated, first-time, coronary artery bypass grafting (CABG) procedures as compared to the control group subjects who did not undergo pericardial closure. Safety was to be established by demonstrating that the composite clinical event rate for the ECM group was not worse than the control group. Effectiveness was to be established by demonstrating a reduced incidence of new onset post-operative atrial fibrillation in the ECM group as compared to the control group. 440 patients at 15 U.S. sites were enrolled between December 2010 and November 2012 and randomized in a 1:1 ratio into either the ECM group (pericardial closure) or the control group (no pericardial closure). A blinded, independent core laboratory evaluated all arrhythmia data to determine if subjects met the effectiveness endpoints. A blinded, independent Clinical Events Committee adjudicated all safety endpoint events. Patients were evaluated at hospital discharge, 30 days and 270 days postoperatively. Subjects were adults (at least 18 years of age) with no prior history of atrial fibrillation or history of anti-arrhythmia drug treatment in the past three months and no implantable cardiac devices (i.e., cardiac resynchronization therapy devices with and without defibrillator capabilities [CRT-Ds and CRTs], implantable cardioverter-defibrillators [ICDs] and pacemakers) undergoing isolated, first-time CABG with a median sternotomy approach.

The primary and secondary effectiveness endpoints, superiority of the ECM over no pericardial closure for reduction in the incidence of new onset post-operative atrial fibrillation, were not met. The study results showed that the rate of new onset post-operative atrial fibrillation for the primary effectiveness endpoint was similar between the two groups, with a rate of 38.3% in the ECM group compared with 35.9% in

effectiveness endpoints, the rate of treated or sustained episodes of new onset post-operative atrial fibrillation (defined as a single episode lasting 15 minutes or more), and the rate of treated episodes of new onset post-operative atrial fibrillation, the results were also similar between the two groups (36.8% versus 35.0% and 27.4% versus 22.1%, respectively, for the ECM group compared with the control group).

The composite primary endpoint event rates for the ECM and control group were 3.9% and 3.7%, respectively. Using the protocol specified non-inferiority margin, 7.5%, the ECM was shown to be non-inferior to control for the primary safety endpoint ( $p < 0.001$ ). Therefore, the primary safety endpoint for the study was achieved. The composite secondary safety event rate was similar for the two groups (5.8% for the ECM group compared with 3.9% for the control group) demonstrating no significant increase in the rate of bypass graft failure in the ECM group compared with the control group.

Although the study failed to demonstrate a reduction in the incidence of new onset post-operative atrial fibrillation, the study demonstrated that the CorMatrix ECM for Pericardial Closure continues to be safe for its intended use, with no significant increase in the rate of bypass graft failure or cardiac tamponade compared with no pericardial closure.

#### ***4.2 Post-market Clinical Evaluation of the ECM for Carotid Repair***

CorMatrix is currently conducting a post-market registry study for the CorMatrix ECM for Carotid Repair (Protocol No. 11-PR-1021). The objective of this registry is to capture and assess device performance data from subjects undergoing patch angioplasty of the carotid artery following carotid endarterectomy using the CorMatrix ECM for Carotid Repair per its commercial Indications for Use. This registry provides an ongoing post-market surveillance mechanism to document clinical outcomes on the use of the CorMatrix ECM for Carotid Repair. This is a multi-center, prospective, single-arm, post-market, observational registry of subjects receiving the CorMatrix ECM for Carotid Repair for patch angioplasty following carotid endarterectomy procedures. This post-market registry may involve up to ten U.S. clinical sites and up to 230 subjects. Data will be collected through the 24-month follow-up.

One-hundred and eighty six patients are enrolled in the study and included in the interim analysis of the CorMatrix ECM for Carotid Repair registry. The data demonstrated that the rate of device related adverse events were consistent with the rates found in the review of the contemporary literature for patch angioplasty. Specifically, no unanticipated events were found and the rate of the events was as anticipated in the risk management plan. Of specific interest in the analysis was the rate of pseudoaneurysm, which was present in 2 (1.08%) of the 186 patients and compared favorably to the rates found in the literature (1.4% to 5%).

The mean carotid stenosis (maximum) at pre-operative was 84.8%. Mean change from baseline values were -56.8%, -57.9%, and -59.6% at the 1 to 3-month, 6-month, and 12-month follow-up evaluations. The mean carotid stenosis (minimum) at pre-operative was 71.7%. Mean change from baseline values were -63.9%, -61.2%, and -63.4% at the 1 to

3-month, 6-month, and 12-month follow-up evaluations. No data are yet available for the 24-month follow-up evaluation, as the first enrollment was on May 24, 2012.

As a result of this analysis and the directed and ongoing risk management activities, the overall residual risk of the CorMatrix ECM for Carotid Repair is determined to be acceptable.

## **5. Study Objectives**

The objective of the study is to actively gather additional information on the use of CorMatrix ECM for pericardial reconstruction.

### Endpoint

The endpoint is defined as the proportion of subjects with device related adverse events.

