## **7. Study Population**

The study population will consist of any subject who has received CorMatrix ECM for pericardial reconstruction. Subjects will be considered enrolled into the study once they have given permission for their medical information to be collected. Before any subject can be enrolled, the IRB for the specific institution must approve the protocol, the informed consent form to be used at that site and a Waiver of Documentation of Consent.

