## 9. Study Procedures

Patients returning for a post-operative visit following a surgical procedure with pericardial reconstruction with CorMatrix ECM will have the following information collected and documented:

- Documentation of the consent process and verbal approval by subject
- Demographic information
- Pre-operative risk factors
- Surgical procedure
- Blood transfusion information, if applicable
- Chest tube placement information
- Surgical complications
- Use of anticoagulation medication
- Cardiac related procedures since surgical procedure
- Device related adverse events

All study-related data will be captured on a standardized Case Report Form. A copy of the Case Report Forms is provided in Appendix A. Case report forms will be sent to CorMatrix via email or mail. Stamped, self-addressed envelopes will be provided.

[name]  
CorMatrix Cardiovascular, Inc.  
[name]  
[name]  
[contact] Direct Office  
[contact]

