## 10. Adverse Event Reporting

### 10.1 Definitions

#### **Adverse Event (AE)**

An adverse event (“AE”) will be defined as any undesirable clinical occurrence in a subject whether it is considered to be device related or not, that includes a clinical sign, symptom, or condition and/or an observation of an unintended technical performance or performance outcome of the device. Causality is defined as not-related, possibly-related, and probably-related to the device. This post market clinical study will collect only events that relate to the use of the CorMatrix ECM as well as any pericardial reconstruction clinical findings.

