## **Appendix D**

### **Investigator Qualifications and Responsibilities**

#### **INVESTIGATOR QUALIFICATIONS AND RESPONSIBILITIES**

Each investigator must be a licensed physician who has received training for using the CorMatrix ECM for the reconstruction and repair of the pericardium. The investigators have the following responsibilities:

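### The only endpoint counts events attributed to the device, so it cannot show an excess of ordinary surgical complications; an any-cause complication proportion should be reported beside it

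*Protocol*

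**What the plan says.** The Study Synopsis and Section 5 of the protocol give a single endpoint: "The endpoint is defined as the proportion of subjects with device related adverse events". Section 1 states the purpose more broadly, saying that the study "will evaluate the safety and effectiveness of CorMatrix ECM for pericardial reconstruction".

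Section 7 defines who is studied: "The study population will consist of any subject who has received CorMatrix ECM for pericardial reconstruction". There is no comparison group. Under Sections 6 and 7, patients are approached at their first follow-up visit and count as enrolled once they give permission there.

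On attribution, Section 10.1 says: "Causality is defined as not-related, possibly-related, and probably-related to the device". It does not say which grades count towards the endpoint. Section 10.3 takes events from the investigator, the subject and the medical records, and no independent or blinded review is described. Appendix D adds: "Each investigator must be a licensed physician who has received training for using the CorMatrix ECM". In the sponsor's earlier randomised trial, by contrast (Section 4.1), "A blinded, independent Clinical Events Committee adjudicated all safety endpoint events".

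Section 10.3 says the potential risks are those of any thoracic operation. It names bleeding, MI, stroke, death, scarring, infection and wound-healing problems. Section 4.1 also discusses tamponade and bypass graft failure.

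The data lists in the Synopsis and Section 9 include surgical complications and "Cardiac related procedures since surgical procedure" as items separate from device-related events, with no relatedness condition. Section 10.1, however, limits event collection to events relating to use of the ECM plus findings on the pericardial reconstruction. Section 11 plans descriptive tables and comparisons with literature and similar studies, without naming the outcome to be compared.

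**The concern.** If the risks are those of ordinary thoracic surgery, any harm from the patch in these event types would appear as a higher rate of events that also occur without it. Someone looking at one patient with bleeding or an infection cannot tell an extra event from a background one. An endpoint that passes through that judgement carries two unknowns, the event rate and the readiness to attribute, and the reported proportion cannot separate them.

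What is at stake is how the result can be read. A low proportion could mean few complications, or many complications that were not attributed. The planned comparison with literature is affected too, because an attributed proportion and an any-cause complication rate are different quantities.

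**Working it through.** The study states no sample size, target rate, significance level or power, so it has no figure of its own to reproduce. All rates below come from the earlier randomised trial in Section 4.1 (440 subjects, 1:1). That trial enrolled isolated first-time CABG and evaluated patients to 270 days, so the numbers are illustrative. I assume 220 per arm, because the analysed denominators are not given.

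**1. Check of the quoted non-inferiority result.** Primary safety composite 3.9% v 3.7%, margin 7.5 points.
- SE = √(0.039×0.961/220 + 0.037×0.963/220) = 0.01823
- z = (0.075 − 0.002)/0.01823 = 4.00, one-sided p = 0.00003, consistent with the stated p < 0.001.

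**2. What that trial leaves open.** Section 4.1 says: "The composite secondary safety event rate was similar for the two groups (5.8% for the ECM group compared with 3.9% for the control group".
- SE = √(0.058×0.942/220 + 0.039×0.961/220) = 0.0205
- Difference = +1.9 points, 95% CI 1.9 ± 1.96×2.05 = about −2.1 to +5.9 (−2.3 to +6.1 with 200 per arm).
- Ratio 5.8/3.9 = 1.49, 95% CI about 0.64 to 3.46.
- Power to detect this difference with 220 per arm is about 15%.

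The interval covers no difference and also a material excess. It establishes neither.

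**3. Why attribution cannot recover an excess.** Suppose, for illustration only, that a difference were causal. The share of events in recipients that is excess is (p_ECM − p_control)/p_ECM.
- Secondary composite: (5.8 − 3.9)/5.8 = 33%.
- Primary composite: (3.9 − 3.7)/3.9 = 5%.

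Even in the larger case, about two events in three would have occurred anyway. With nothing else to distinguish them, no single event would be more likely than not due to the device.

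**4. What the endpoint would read.** Let s be the share of such events called device-related, the same for background and excess events because they look alike. The endpoint reads s × rate.

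| s | rate 3.9% | rate 5.8% |
|---|---|---|
| 5% | 0.20% | 0.29% |
| 10% | 0.39% | 0.58% |
| 25% | 0.98% | 1.45% |

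Moving s from 10% to 25% changes the figure more than moving the rate from 3.9% to 5.8%. Because s is unknown, the two cannot be told apart.

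**5. What an any-cause proportion adds, and its limit.** It does not depend on s. With 58 events in 1,000 subjects (an assumed size), the exact 95% CI is 4.4% to 7.4%. It does not show an excess by itself. Against a fixed external rate, with a true rate of 5.8%, 1,000 subjects and one-sided 0.025, exact power is 0.99 if the external rate is 3.0%, 0.81 at 3.9% and 0.19 at 5.0%. At 6.0% there is no excess to find, and the chance of rejection is about 0.01. The conclusion therefore depends on choosing a comparable external rate.

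**6. Whether the data will exist.** Section 9 and the Synopsis list complications and later procedures unfiltered, while Section 10.1 restricts collection to ECM-related events and reconstruction findings. The case report form in Appendix A is a separate document and not at hand, so which of the two governs cannot be settled from the text. In addition, the follow-up items in Section 10.2 grade relationship to the procedure or surgery, not to the device.

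**The case against.** The strongest reply is that the limitation belongs to a single-arm study, not to the endpoint's wording: an any-cause proportion without a control cannot show an excess either. That stands, as step 5 shows, and the added figure should carry that caveat. It still removes one of the two unknowns and is the right quantity to set beside published complication rates.

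A second reply is that the study is descriptive, its objective is only to gather information, and Section 11 may tabulate complications anyway, with the list left to an analysis plan. In part this stands. But the endpoint and the scope of event collection are fixed in the protocol, and no analysis plan can recover events that Section 10.1 kept off the form.

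Third, the definition of an adverse device event in Section 10.1 is broad: it rests on a reasonable possibility and covers the procedure and the presence of the device. Device-specific failures can be attributed, and ordinary complications are not excluded by definition. So a reader who inferred that the endpoint measures nothing but willingness to blame the device would go too far. The breadth does, however, increase the dependence on grading.

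A reader might also infer that the earlier trial shows harm, or that a third of events in recipients are due to the device. The documents do not support this: the interval spans zero, the primary composite was 3.9% v 3.7% and met its margin, and the population and follow-up differ from those here. Nor do the documents state that the form already captures unfiltered complications, or who assigns causality. That the assessor knows the exposure is an inference from every subject having the device.

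**Conclusion.** The point holds in a limited form. The sole endpoint is an attributed proportion in an all-exposed study with no adjudication described, and the protocol itself says the risks are those of ordinary thoracic surgery. For those event types the endpoint cannot distinguish more harm from readier attribution. The size of the problem in this study cannot be computed. The illustration shows only that plausible differences in attribution can outweigh a 1.5-fold difference in event rate, on the assumptions of 220 per arm, rates borrowed from an isolated-CABG trial, and equal attribution of background and excess events.

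An any-cause proportion would be free of grading, but it is not a full measure of harm in recipients. It shows an excess only relative to a comparable external rate. Because patients are enrolled at the first visit, those who died or did not return before it are in neither numerator nor denominator. This is a worthwhile, low-cost improvement and does not invalidate the study.

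**What to change.** - Keep the device-related proportion, and state in Section 5 that it is an attribution figure and not the excess risk due to the device.
- Add beside it, in Sections 5 and 11, the proportion of subjects with any of a fixed list of complications by the visit, regardless of causality grade. The list can come from events the protocol already names (tamponade, graft failure, bleeding, infection or wound complication, MI, stroke) plus any repeat cardiac procedure. Death is not listed because subjects are enrolled in person at the visit.
- Reconcile Section 10.1 with Section 9 and the Synopsis so that these events are collected whatever their relatedness.
- Name the any-cause figure as the one used for the literature comparison in Section 11. State that it shows an excess only relative to a comparable external rate, and that it excludes patients who died or did not return before the visit.

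The cost is protocol wording, one more table and possibly named tick-boxes on the form, with no new visit or procedure. The any-cause figure will be higher and look less favourable than the attributed one.
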